4.4 Treatments

4.4.1 Treatment Groups

During the PCI procedure the Dynamic Coronary Roadmap study device will be used for the randomly selected subjects in the DCR group. For the randomly selected subjects in the control group Dynamic Coronary Roadmap will not be used in order to serve as the comparator to measure the effect of Dynamic Coronary Roadmap. Standard of care will be applied to all subjects.

There are no additional devices or medications required for the study. Physician investigators participating in this study are expected to follow their normal clinical practice in treating and following up patients with Coronary Artery Disease (CAD). Patients randomized to the DCR group will undergo a PCI procedure during which DCR is used while those randomized to the control group will undergo PCI without the use of DCR. The preparation of the PCI procedure, the procedure itself and follow up will be performed following standard of care.

4.4.2 Randomization

The randomization will be performed via the Electronic Data Capture (EDC) system hosting the electronic Case Report Form.

In order to ensure balance of the treatment groups across subgroups, we stratified the randomization by site and within site by type of PCI (ad hoc or elective) and the number of vessels to be treated via PCI, i.e., 1, 2, or 3 or more vessel PCI. Within the subgroups we will perform a permuted block design. We will use a block size of 4 patients per block. There will be an equal allocation to the PCI procedure with DCR and the PCI procedure without the use of DCR (1:1 randomization).

In case of elective PCI, randomization will be done before the procedure and in case of ad hoc PCI randomization will be done upon decision to go for PCI right after diagnostics, so when the patient on the table still.

In enrolled subjects the investigator pre procedurally deemed no usage of OCT and/or the rotational or orbital atherectomy is required. During the PCI procedure usage of OCT and/or rotational or orbital atherectomy is left to the investigator's discretion.

In the case OCT and/or rotational or orbital atherectomy is used in enrolled subjects, these subjects will be replaced. When the decision is made to replace a subject this subject will not count for the required total number of subjects total, but will still be part of the Safety population. A new subject will be randomized to either of the arms.

Document ID:	<As applicable, per local requirements>	Document title:		Classification:	For internal use
		Statistical Analysis Plan			
Modified:	11MAY2023	Template ID:	ClinicalStudyTemplate0025	Author:	
Version:	3.0	Template Version Date:	02MAR2018	Approver:	
Status:	Final			Page:	11 of 52

Statistical Analysis Plan

Thus, the following subjects will be replaced:

- Subjects undergoing PCI supported by OCT will be replaced.
- Subjects undergoing PCI supported by rotational or orbital atherectomy will be replaced.

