4.3.1 Inclusion Criteria

- Subject is undergoing Percutaneous Coronary Intervention (PCI) with a degree of complexity that anticipates the need for more than 25ml of iodinated contrast volume
- Subject has signed informed consent
- Subject is 18 years of age or older, or of legal age to give informed consent per state or national law

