4.5 Control to Minimize Bias

Ideally the study should be blinded, because there is potential intrinsic bias (sometimes referred to as the Hawthorne Effect) due to the fact the participants know that they are participating in a clinical study and know which arm they are participating in. However, as the Dynamic Coronary Roadmap is a visualization tool the study cannot be blinded.

Only standard guiding catheters will be used in the study and devices that could potentially confound contrast usage (e.g. rotational or orbital atherectomy device) will be excluded.

The methods to check whether the PCI was successful can include angiography, Stent Boost, and/or IntraVascular UltraSound (IVUS). Some of these procedures can include contrast agent volume, whereas others specifically do not (e.g., Stent Boost is a software feature). Therefore, the choice for checking the PCI result could introduce a bias based on individual users' preferences. Some PCI check methods are potential confounders for contrast usage and we will investigate to take measures to reduce the risk of bias based on site differences and user preferences. During site initiation it has been communicated that the PCI check procedure is to be standardized in both arms, which is standard of practice. This will be checked via remote monitoring of the eCRFs.

Analyses to determine whether there is an effect based on e.g. intervention difficulty (measured by the SYNTAX score), lesion characteristics, patient demographics, physician experience, center effect etc. will be performed. If an effect is found applying adjustment analysis, i.e. analysis of covariance adjusting for relevant confounders will be considered as a sensitivity analysis.

Document ID:	<As applicable, per local requirements>	Document title:	Classification:	For internal use
Modified:	11MAY2023	Statistical Analysis Plan		
Version:	3.0	Template ID:	ClinicalStudyTemplate0025	Approver:
Status:	Final	Template Version Date:	02MAR2018	Page: 12 of 52

Statistical Analysis Plan

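### A single fixed block size of 4 within site-level strata of an unblinded trial leaves an avoidable opportunity for selection bias: up to one third of allocations are certain to anyone who knows the block size and tracks the stratum

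*SAP*

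**What the plan says.** SAP 4.4.2 describes the strata: "we stratified the randomization by site and within site by type of PCI (ad hoc or elective) and the number of vessels to be treated", in three vessel categories. It then states: "Within the subgroups we will perform a permuted block design", and "We will use a block size of 4 patients per block". Allocation is 1:1, so each block holds two DCR and two control places. On the mechanism it says: "The randomization will be performed via the Electronic Data Capture (EDC) system hosting the electronic Case Report Form". Elective cases are randomised before the procedure. Ad hoc cases are randomised once diagnostics are done and PCI has been chosen.

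SAP 4.5 accepts that the trial is open: "However, as the Dynamic Coronary Roadmap is a visualization tool the study cannot be blinded". It discusses the Hawthorne effect and the choice of PCI check method as sources of bias, but not the predictability of allocation. SAP 4.3.1 admits a patient whose PCI is one "with a degree of complexity that anticipates the need for more than 25ml of iodinated contrast volume". SAP 8.1.1 allows at most three investigators per centre.

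Protocol 6.1 mentions stratification by PCI type and number of vessels only. It gives neither site stratification nor a block size. Neither document describes varying the block size or withholding it from sites.

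**The concern.** Central randomisation hides the list. It does not hide what past open allocations imply about the next one. In a block of four, once two patients have gone to one arm, every remaining place belongs to the other.

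This matters because operators use judgement before allocation. The 25 ml criterion is a forecast of the primary outcome itself. The vessel count that selects the stratum is a plan. In ad hoc cases much of the difficulty is already visible when the patient is randomised. A site that expects DCR next could, even without intent, enter an easier case, or plan the vessels so that the case falls in a different stratum. Contrast volume depends on case difficulty, so such steering would shift the difference in means. The primary test is an unadjusted t-test and would not correct for it.

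**Working it through.** **Inputs.** From SAP 4.4.2: block of 4, 1:1, and 2 PCI types × 3 vessel categories = 6 strata per site. From SAP 8.1: 394 subjects and at least 5 centres, hence at least 30 strata. From SAP 8.1.1: SD 73.0 ml and planned difference 152.1 − 129.3 = 22.8 ml. From SAP 8.1.2: 177 per group after 10% dropout. The documents give no figure for predictability, so there is none to reproduce.

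**Completed blocks.** Two DCR and two control places have 6 possible orders, which gives 24 positions. An allocation is certain when only one arm has places left. The probabilities at positions 1 to 4 are 0, 0, 1/3 and 1. The mean is (0 + 0 + 1/3 + 1)/4 = 8/24 = 33.3%. Guessing the arm with more places left is right 17/24 = 70.8% of the time, against 50% by chance.

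**Unfilled blocks.** At 5 sites a stratum averages 394/30 = 13 subjects, and at 15 sites 394/90 = 4.4, so many last blocks stay open. Simulating 394 subjects over equal-sized sites gives 24-30% certain across 5 to 15 sites. The table uses strata skewed 40/8/2% over the vessel categories within each PCI type, at 5 to 15 sites. The observer knows the possible block sizes and sees every allocation in the stratum. Site number and stratum shares are assumptions.

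| Block sizes | Certain | Best guess right |
|---|---|---|
| 4 | 26-30% | 67-69% |
| 4 and 6 | about 5% | 65-68% |
| 4, 6 and 8 | about 2% | 64-67% |

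With equal strata and 15 sites, the share for a fixed block of 4 falls to 24%.

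**What steering could do (illustration only).** Suppose that operators act only when the next arm is certain, a share c of allocations. Suppose also that they place cases d ml easier than average in DCR and d ml harder in control. The spurious difference is 2 × c × d. With c = 0.24 to 0.30:

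- d = 5 ml gives 2.4 to 3.0 ml.
- d = 10 ml gives 4.8 to 6.0 ml.

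The largest value is 6.0/22.8 = 26% of the planned effect. The standard error is 73 × √(2/177) = 7.76 ml. With no true effect, the one-sided error is 1 − Φ(1.96 − bias/7.76). It rises from 2.5% to about 5% at 2.4 ml and about 12% at 6.0 ml. Nothing in the documents supports a particular d. This shows only that modest steering would matter.

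**The case against.** **Foreknowledge is assumed.** The protocol omits the block size, and the SAP that states it is marked for internal use. Inference from the sequence means finding unmarked block boundaries in strata that may hold only a few blocks, with up to three operators interleaved. Suppose three operators share cases equally and each sees only their own patients. Even an operator who knows the block size and position is then certain in only (1/3 × 1/9 + 1/9)/4 = 3.7% of allocations in completed blocks. This stands as a limit: the one-third figure needs pooled tracking within a site. Such tracking is feasible with at most three investigators, and the documents do not say that sites are kept unaware.

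**There are traces and checks.** Consent precedes enrolment, and SAP 8.3 and the table list report disposition and screen failures, so dropping a consented patient would be visible. SAP 8.4 and 8.14 compare baseline characteristics and allow ANCOVA for SYNTAX score, lesion characteristics, physician experience and centre. These are partial safeguards. Adjustment is conditional, is a sensitivity analysis, and reaches only recorded factors. A reader might infer that steering could never be detected or corrected, but these provisions do not support so strong a reading.

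**Varied blocks barely change the best guess.** True: it falls by about 2 to 4 points. The gain lies in removing nearly all certain allocations.

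**Short blocks serve balance.** Also true, and balance is the SAP's stated purpose. The cost of varying the size is small.

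**Conclusion.** The plan leaves an avoidable opportunity for selection bias. Up to one third of allocations are certain in advance: 33% in completed blocks, about 24-30% with unfilled blocks. This rests on an assumed 5 to 15 equal-sized sites, and on an observer who knows or infers the block size and follows every allocation in the stratum.

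Two stronger readings are tempting. One is that a third of allocations were in fact known at the sites. The documents do not say who knew the block size or whether anyone tracked allocations. The other is that the primary comparison is biased. The documents show discretion before randomisation and a predictable sequence, and no evidence that either was exploited. The millilitre and type I error figures depend on an assumed degree of steering and are not estimates for this trial.

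**What to change.** **If randomisation is still open:** replace the single block size in SAP 4.4.2 with sizes drawn at random (for example 4 and 6, or 4, 6 and 8), and state that they are withheld from sites. This takes one EDC setting and one sentence. The largest within-stratum imbalance rises from 2 to 3 or 4, and in simulation the mean overall arm imbalance rises by about 0.4 to 1.4 patients. Sample size is unchanged.

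**If enrolment is complete:** this is plausible, though the documents do not state it. SAP version 3.0 is dated May 2023, enrolment was planned for 9 months, and 4.4.2 describes stratification in the past tense. In that case add a sensitivity analysis to SAP 8.11.1:

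1. From the full randomisation sequence, including replaced subjects, compute p = DCR places left in the block / all places left, just before each subject's allocation.
2. Refit the primary comparison with p as a covariate.
3. Within each arm, test whether p predicts contrast volume and SYNTAX score. Without selection it should not.

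No new data are needed. The cost is precision, because p is correlated with treatment. In completed blocks the variance of p is (0 + 1/36 + 1/12 + 1/4)/4 = 0.0903, against 0.25 for treatment, so R² = 0.361. The standard error grows by a factor of about 1/√(1 − 0.361) = 1.25. Judge the result by whether the estimate moves, not by whether it stays significant.

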4.5 Control to Minimize Bias

Ideally the study should be blinded, because there is potential intrinsic bias (sometimes referred to as the Hawthorne Effect) due to the fact the participants know that they are participating in a clinical study and know which arm they are participating in. However, as the Dynamic Coronary Roadmap is a visualization tool the study cannot be blinded.

Only standard guiding catheters will be used in the study and devices that could potentially confound contrast usage (e.g. rotational or orbital atherectomy device) will be excluded.

The methods to check whether the PCI was successful can include angiography, Stent Boost, and/or IntraVascular UltraSound (IVUS). Some of these procedures can include contrast agent volume, whereas others specifically do not (e.g., Stent Boost is a software feature). Therefore, the choice for checking the PCI result could introduce a bias based on individual users' preferences. Some PCI check methods are potential confounders for contrast usage and we will investigate to take measures to reduce the risk of bias based on site differences and user preferences. During site initiation it has been communicated that the PCI check procedure is to be standardized in both arms, which is standard of practice. This will be checked via remote monitoring of the eCRFs.

Analyses to determine whether there is an effect based on e.g. intervention difficulty (measured by the SYNTAX score), lesion characteristics, patient demographics, physician experience, center effect etc. will be performed. If an effect is found applying adjustment analysis, i.e. analysis of covariance adjusting for relevant confounders will be considered as a sensitivity analysis.

Document ID:	<As applicable, per local requirements>	Document title:	Classification:	For internal use
Modified:	11MAY2023	Statistical Analysis Plan		
Version:	3.0	Template ID:	ClinicalStudyTemplate0025	Approver:
Status:	Final	Template Version Date:	02MAR2018	Page: 12 of 52

Statistical Analysis Plan

5 EFFICACY AND SAFETY VARIABLES

5.1 Efficacy and Safety Measurements

The following efficacy and safety measurements will be performed:

Efficacy measurements

Total undiluted iodinated contrast volume (in ml) used per PCI procedure (from first positioning the interventional guiding catheter in stable coronary position till end of PCI procedure) measured by an automatic contrast injector. Any contrast use prior to getting access (e.g. for balloon preparation or contrast injector flushing) should not be counted in the total contrast volume, i.e., the contrast injector should be zeroed just prior to getting access if not zero already. Furthermore, during the PCI procedure any contrast use not injected into the patient, e.g. used for device preparation, should not be counted in the total PCI contrast volume.

Total number of contrast enhanced cine angiographic X-ray runs (angiograms) determined via visual assessment (e.g., on the Philips X-ray system) per PCI procedure (from first positioning the interventional guiding catheter in stable coronary position till end of PCI procedure).

Incidence of Acute Kidney Injury (AKI) at discharge following standard clinical care. AKI is defined as [Parsh 2016, Bellomo 2004]:

- an absolute Serum Creatinine (SCr) increase >0.3 mg/dl within 48 hours post PCI or a relative SCr increase $>50\%$ within 7 days post PCI
OR
- eGFR decrease $>25\%$ within 48 hours post PCI

The total fluoroscopy and procedure time per PCI (from first positioning the interventional guiding catheter in stable coronary position till end of PCI procedure), where the fluoroscopy time is measured by the Philips X-ray system.

The total X-ray dose (DAP, AK) related to PCI (from first positioning the interventional guiding catheter in stable coronary position till end of PCI procedure). The total DAP and AK per PCI is measured by the Philips X-ray system.

Procedural success, defined as an open target vessel with a maximum of 30% residual stenosis and TIMI flow grade 3 (complete perfusion) [TIMI 1985], e.g. determined via visual inspection of Coronary Angiography.

Document ID:	<As applicable, per local requirements>	Document title:		Classification:	For internal use
		Statistical Analysis Plan			
Modified:	11MAY2023			Author:	
Version:	3.0	Template ID:	ClinicalStudyTemplate0025	Approver:	
Status:	Final	Template Version Date:	02MAR2018	Page:	13 of 52

Statistical Analysis Plan

In-hospital Major Adverse Cardiovascular and Cerebral Events (MACCE) are collected in the eCRF. MACCE is defined as one or more of the following events: All cause death, Acute Myocardial Infarction (AMI), Coronary Artery Bypass Grafting (CABG), Repeat Coronary Revascularization of the target lesion, Acute Ischemic Stroke (AIS) during hospitalization for the PCI procedure.

Safety Measurements

Serious adverse events and device deficiencies that could have led to a serious adverse device effect are reported to the sponsor without unjustified delay.

5.2 Appropriateness of Measurements

The endpoints are appropriate for measuring the stated efficacy and safety.

However the following restrictions for Serum Creatinine/EGFR and Acute Kidney Injury should be taken into account.

SCr/eGFR

According to [Guideline NVvR 2017] the measurement of SCr/eGFR is valid for:

- Maximally 7 days when the patient has an acute disease or an acute deterioration of a chronic disease;
- Maximally 3 months when the patient has a known chronic disease with stable renal function;
- Approximately 12 months in all other patients.

Acute Kidney Injury

The majority of PCI patients are discharged within 24 hours after the PCI procedure and consequently the SCr measurement is performed within 24 hours post PCI while the SCr levels might still be rising and diagnosis of AKI may be missed as a result.

Document ID:	<As applicable, per local requirements>	Document title:	Classification:	For internal use
Modified:	11MAY2023	Statistical Analysis Plan	Author:	
Version:	3.0	Template ID: ClinicalStudyTemplate0025	Approver:	
Status:	Final	Template Version Date: 02MAR2018	Page:	14 of 52

Statistical Analysis Plan

5.3 Efficacy Variables

5.3.1 Primary Efficacy Variables

The primary efficacy variable is the total undiluted iodinated contrast volume (in ml) used per PCI (from first positioning the interventional guiding catheter in stable coronary position till end of PCI procedure) measured by an automatic contrast injector.

5.3.2 Secondary Efficacy Variables

The secondary efficacy variable is the total number of contrast enhanced cine angiographic X-ray runs (angiograms) per PCI (from first positioning the interventional guiding catheter in stable coronary position till end of PCI procedure) determined via visual assessment (e.g., on the Philips X-ray system).

5.3.3 Exploratory Efficacy Variables

The exploratory efficacy variables are:

- The average undiluted iodinated contrast volume (in ml) used per vessel PCI measured by an automatic contrast injector. For multi vessel PCI the iodinated contrast volume used per vessel PCI will be determined based on the total PCI contrast volume divided by the number of vessels treated by PCI.
- Total iodinated contrast volume (in ml) stratified by 1 vessel PCI, 2 vessel PCI and 3 or more vessel PCI.
- Total iodinated contrast volume (in ml) stratified by simple, intermediate and complex PCI (according to the SYNTAX score for the vessel(s) treated with PCI).
- Incidence of Acute Kidney Injury (AKI) at discharge following standard clinical care. AKI is defined as an absolute Serum Creatinine (SCr) increase >0.3 mg/dl within 48 hours post PCI or a relative SCr increase $>50\%$ within 7 days post PCI, or eGFR decrease $>25\%$ within 48 hours post PCI.
- Variability of the total iodinated contrast volume (in ml) used per PCI measured by an automatic contrast.
- The total fluoroscopy and procedure time per PCI, where the fluoroscopy time is measured by the Philips X-ray system.
- The total X-ray dose (DAP, AK) related to PCI. The total DAP and AK per PCI is measured by the Philips X-ray system.

Document ID:	<As applicable, per local requirements>	Document title:		Classification:	For internal use
		Statistical Analysis Plan			
Modified:	11MAY2023			Author:	
Version:	3.0	Template ID:	ClinicalStudyTemplate0025	Approver:	
Status:	Final	Template Version Date:	02MAR2018	Page:	15 of 52

Statistical Analysis Plan

- Procedural success, defined as an open target vessel with a maximum of 30% residual stenosis and TIMI flow grade 3 (complete perfusion) [TIMI 1985], e.g. determined via visual inspection of Coronary Angiography.
- In-hospital Major Adverse Cardiovascular and Cerebral Events (MACCE). MACCE is defined as one or more of the following events: All cause death, Acute Myocardial Infarction (AMI), Coronary Artery Bypass Grafting (CABG), Repeat Coronary Revascularization of the target lesion, Acute Ischemic Stroke (AIS) during hospitalization for the PCI procedure.

All parameters assessed during PCI are measured from first positioning the interventional guiding catheter in stable coronary position till end of PCI procedure.

5.4 Safety Variables

Adverse events and device deficiencies are reported through the Philips Vigilance Reporting System. MACCE, duration until discharge (in days) and laboratory assessments will be assessed in the CRF.

6 DEFINITIONS

Baseline is defined as last value prior to randomisation. Baseline values may be recorded at Screening if there is no other result prior to randomisation.

Duration (days) will be calculated as follows:

- Duration = last observation date – first observation date +1

Duration of procedure (minutes) will be calculated as stop date/time of PCI procedure minus the start date/time of the PCI procedure from first positioning the interventional guiding catheter in stable coronary position.

Document ID:	<As applicable, per local requirements>	Document title:	Classification:	For internal use
Modified:	11MAY2023	Statistical Analysis Plan	Author:	
Version:	3.0	Template ID: ClinicalStudyTemplate0025	Approver:	
Status:	Final	Template Version Date: 02MAR2018	Page:	16 of 52

Statistical Analysis Plan

Duration until discharge (days)

Duration until discharge = discharge date – PCI procedure date +1

Study Day is defined as follows:

- If study date < randomisation date then study day = study date – randomisation date
- If study date >= randomisation date then study day = study date – randomisation date + 1

Physician Experience is defined as the number of years of experience post-fellowship.

Body Mass Index (BMI)

$$\text{BMI} \left(\frac{\text{kg}}{\text{m}^2} \right) = \frac{\text{Weight (kg)}}{\text{Height(m)}^2}$$

Incidence of Acute Kidney Injury (AKI) is defined as

- an absolute Serum Creatinine (SCr) increase >0.3 mg/dl within 48 hours post PCI or a relative SCr increase >50% within 7 days post PCI

OR

- or eGFR decrease >25% within 48 hours post PCI

Procedural success is defined as an open target vessel with a maximum of 30% residual stenosis and TIMI flow grade 3 (complete perfusion) [TIMI 1985], e.g. determined via visual inspection of Coronary Angiography.

Estimated Glomerular Filtration Rate

Using the SCr measurement often the estimated GFR (eGFR) is determined as a measure of kidney function, which can be calculated according to the Modification of Diet in Renal Disease (MDRD) equation or its successor the Chronic Kidney Disease epidemiology (CKD-EPI) equation [Levey 1999, Bellomo 2004, Levey 2006, Levey 2009, Van den Brand 2011, Nyman 2014]. The CKD-EPI equation to estimate the glomerular filtration rate reads [Levey 2009]:

Document ID:	<As applicable, per local requirements>	Document title:		Classification:	For internal use
Modified:	11MAY2023	Statistical Analysis Plan			Author: [REDACTED]
Version:	3.0	Template ID:	ClinicalStudyTemplate0025	Approver: [REDACTED]	
Status:	Final	Template Version Date:	02MAR2018	Page:	17 of 52

Statistical Analysis Plan

The Chronic Kidney Disease epidemiology (CKD-EPI) equation to estimate the glomerular filtration rate reads [Levey 2009]:

$$eGFR = 141 * \min(SCr/K, 1)^\alpha * \max(SCr/K, 1)^{-1.209} * 0.993^{Age} * 1.018 \text{ [if female]} \times 1.159 \text{ [if black]},$$

with $K=0.7$ and $\alpha=-0.329$ if female;
with $K=0.9$ and $\alpha=-0.411$ if male.

In which SCr is Serum Creatinine. Here min indicates the minimum of SCr/K or 1, and max indicates the maximum of SCr/K or 1.

Based on the eGFR calculation Chronic Kidney Disease (CKD) can be classified in 5 stages [Tsai 2014a].

CKD classification	eGFR (ml/min/1.73m ²)
Stage I (normal renal function)	>=60
Stage II (mild – moderate reduction)	45 – < 60
Stage III (moderate – severe reduction)	30 – < 45
Stage IV (severe reduction)	15 - < 30
Stage V (renal failure)	<15

Table 1 CKD classification based on eGFR

Contrast volume (V) to creatinine clearance GFR ratio

The contrast volume (V)/eGFR ratio will be calculated by dividing the volume of contrast volume (in ml) received by the patients' eGFR (in ml/min/1.73m²).

MACCE

In-hospital Major Adverse Cardiovascular and Cerebral Events (MACCE). MACCE is defined as one or more of the following events: All cause death, Acute Myocardial Infarction (AMI), Coronary Artery Bypass Grafting (CABG), Repeat Coronary Revascularization of the target lesion, Acute Ischemic Stroke (AIS) during hospitalization for the PCI procedure.

Document ID:	<As applicable, per local requirements>	Document title:	Classification:	For internal use
		Statistical Analysis Plan		
Modified:	11MAY2023		Author:	
Version:	3.0	Template ID:	ClinicalStudyTemplate0025	Approver:
Status:	Final	Template Version Date:	02MAR2018	Page: 18 of 52

Statistical Analysis Plan

The **SYNTAX score** [Sianos 2005, Neumann 2018] will be determined for each vessel treated with PCI as an index for anatomical complexity of the PCI, see Figure below and Appendix 1.

The vessel SYNTAX score calculates a point value for each vessel treated with PCI. The patients' overall SYNTAX score will be derived as the maximum value across all treated vessels.

The patients' overall SYNTAX score will be divided into tertiles as an index for complexity of the PCI procedure. We will label these groups as Complexity 1st Tertile, Complexity 2nd Tertile and Complexity 3rd Tertile.

Step 1 Dominance: determine right or left coronary artery dominance

Step 2 Coronary segment: each diseased coronary segment is assigned a weight depending on its location

Segment No	Right dominance	Left dominance
1 RCA proximal	1	0
2 RCA mid	1	0
3 RCA distal	1	0
4 Posterior descending artery	1	n.a.
16 Posterolateral branch from RCA	0.5	n.a.
16a Posterolateral branch from RCA	0.5	n.a.
16b Posterolateral branch from RCA	0.5	n.a.
16c Posterolateral branch from RCA	0.5	n.a.
5 Left Main	5	6
6 LAD proximal	3.5	3.5
7 LAD mid	2.5	2.5
8 LAD apical	1	1
9 First diagonal	1	1
9a First diagonal ^a	1	1
10 Second diagonal	0.5	0.5
10a Second diagonal ^a	0.5	0.5
11 Proximal circumflex artery	1.5	2.5
12 Intermediate/ anterolateral artery	1	1
12a Obtuse marginal ^a	1	1
12b Obtuse marginal ^b	1	1
13 Distal circumflex artery	0.5	1.5
14 Left posterolateral	0.5	1
14a Left posterolateral ^a	0.5	1
14b Left posterolateral ^b	0.5	1
15 Posterior descending	n.a.	1

Document ID:	<As applicable, per local requirements>	Document title:		Classification:	For internal use
		Statistical Analysis Plan			
Modified:	11MAY2023	Template ID:	ClinicalStudyTemplate0025	Author:	
Version:	3.0	Template Version Date:	02MAR2018	Approver:	
Status:	Final			Page:	19 of 52

Statistical Analysis Plan

Step 3	Diameter stenosis	
The score of each diseased coronary segment is multiplied by two in case of a stenosis 50-99% and by five in case of total occlusion.
 
In case of total occlusion, additional points will be added as follows:
 
 - Age >3 months or unknown +1 - Blunt stump +1 - Bridging +1 - First segment visible distally +1 per non-visible segment - Side branch at the occlusion +1 if <1.5 mm diameter +1 if both <1.5 mm and >1.5 mm diameter +0 if ≥1.5 mm diameter (i.e. bifurcation lesion)
Step 4	Trifurcation lesion	
The presence of a trifurcation lesion adds additional points based on the number of diseased segments:
 
 - 1 segment +3 - 2 segments +4 - 3 segments +5 - 4 segments +6
Step 5	Bifurcation lesion	
The presence of a bifurcation lesion adds additional points based on the type of bifurcation according to the Medina classification:126
 
 - Medina 1,0,0-1,0-1,0 +1 - Medina 1,1,1-0,0,1-1,0,1-0,1,1 +2 
Moreover, the presence of a bifurcation angle <70° adds one additional point

Step 6	Aorto-ostial lesion	The presence of aorto-ostial lesion segments adds one additional point
Step 7	Severe tortuosity	The presence of severe tortuosity proximal of the diseased segment adds two additional points
Step 8	Lesion length	Lesion length >20 mm adds one additional point
Step 9	Calcification	The presence of heavy calcification adds two additional points
Step 10	Thrombus	The presence of thrombus adds one additional point
Step 11	Diffuse disease/ small vessels	The presence of diffusely diseased and narrowed segments distal to the lesion (i.e. when at least 75% of the length of the segment distal to the lesion has a vessel diameter <2 mm) adds one point per segment number

SYNTAX: Synergy between Percutaneous Coronary Intervention with TAXUS and Cardiac Surgery

Figure 1 Steps to determine SYNTAX score as an index for anatomical complexity of the PCI [from Neumann 2018]

